9. WHO Recommendations for the Prevention and Treatment of Postpartum Haemorrhage. Geneva: World Health Organization; 2012.
10. WOMAN Trial Collaborators. Effect of early tranexamic acid administration on mortality, hysterectomy, and other morbidities in women with post-partum haemorrhage (WOMAN): an international, randomised, double-blind, placebo-controlled trial. Lancet. 2017 Apr 26.

Research Design:

a. General Approach: Prospective Cohort study

b. Description: Phase 4

c. Methods: One Arm

d. Statistical Analysis:

- SPSS software will be used for our statistical analysis. Normal distribution will be assumed given the intended number of patients for analysis. Categorical variables will be analyzed using the Chi-square test. The t-test will be utilized for the comparison of continuous interval data.

-Using postpartum hemorrhage rate of 2.86% (institutional data), and a desired impact of reducing the hemorrhage rates by 50% after implementation of the new protocol, then 890 subjects would need to be recruited to answer the question.

e. Safety Analysis Plan:

- Data collection for each participant will occur in real time during pre and post delivery times, therefore safety monitoring of the patient and data will be simultaneous.
- A Research monitor has been appointed to oversee the safe and ethical conduct of the study. Additionally, the Research Monitor will provide review and comment on any adverse events. The Research Monitor is not a member of the investigative team. The role of the Research Monitor is as follows:
 1. monitor the consent process to ensure an absence of coercion
 2. monitor data collection/clinical outcome
 3. review all adverse event reports with comments from the PI and forward to the IRB with his/her own comments. Adverse events must be received by the IRB within 5 business days of occurrence or reporting (within 24 hours for serious adverse events)
 4. ensure the inclusion/exclusion criteria are followed
 5. review data security measures
- Any emerging safety concerns to include any adverse event rate higher than this institution's historical average will result in a halt to the study.

Subject Population:

Pregnant women presenting for delivery at NMCSO

a. Exclusion/Inclusion criteria:

Exclusion:

- a. Age less than 18 years
- b. Planned cesarean hysterectomy
- c. Current anticoagulant use
- d. Subarachnoid hemorrhage
- e. Any active/current intravascular clotting (i.e. venous thromboembolic events)

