 2. For patients that present for delivery at a gestational age less than 34 weeks, it will be recommended that they discard their breast milk until 24 hours after their last TXA administration.
 3. Order TXA for patient in ESSENTRIS
 4. RN to pull TXA from Pyxis and put in patient's room
 5. TXA per protocol (see supplement A)
 6. The use of additional uterotonics or single additional dose of TXA is at the discretion of the delivering provider
 7. For patient monitoring protocol please see Supplement B.
 8. All neonates are monitored for a minimum of 24 hours either by the NICU or the Newborn Nursery. Vitals are taken every four hours. Weights and bilirubin levels are obtained daily. Daily physical exams are performed.
3. Data collection
 1. Participants will be assigned an individualized subject number upon their enrollment to the study.
 2. Participants will be followed from their enrollment into the study until six weeks postpartum.
 3. An Excel spreadsheet will be used to collect the variables as listed above.
 4. Once the variable collection is complete, the information will become de-identified.

5. Chart review will be performed to estimate institutional rates of the secondary outcomes in the 12 months preceding the initiation of the protocol.
4. Data Analysis
 1. SPSS software will be used for our statistical analysis. Normal distribution will be assumed given the intended number of patients for analysis. Categorical variables will be analyzed using the Chi-square test. The t-test will be utilized for the comparison of continuous interval data.
 2. Using a postpartum hemorrhage rate of 2.86% (institutional data), and a desired impact of reducing the hemorrhage rates by 50% after implementation of the new protocol, then 890 subjects would need to be recruited to answer the question.
 3. The secondary outcomes will also be tested against institutional rates. Institutional rates will be estimated by record sampling done at the time of data collection.

Experimental Procedures:

See supplement A

Research materials collected:

Variables to be collected:

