Age, race/ethnicity, DoD status, BMI, gestational age, # of fetuses, gravidity, parity, admission diagnoses, admission estimated fetal weight, intrapartum diagnoses, postpartum diagnoses, misoprostol use, oxytocin use, mechanical dilation, duration of labor, magnesium sulfate use, planned mode of delivery, mode of delivery, birth weight, indication for operative delivery, neonatal outcomes, maternal outcomes, admission to the intensive care unit, uterotonic use, mechanical tamponade, blood product transfusion, estimated blood loss, qualitative blood loss, cumulative blood loss, laboratory results, post-delivery laboratory results

Confounding variables:

Management of the 3rd stage of labor

Source of the data:

Outpatient records (AHLTA), Inpatient records (Essentris). As providers, the investigators have access to these systems as a standard of care for patients receiving care from investigator-providers.

Paper records created in the Labor and Delivery department during the course of a delivery.

The data collected will be measured against the historic PPH rates of NMCSO over a period of time to be determined.

Protection of Privacy:

Each participant will be given a unique study number. A master list with only the minimal Personal Identifiable Information (PII) needed for follow up and their study number will be kept in the PI's office on a CAC PIN protected computer in the PI's locked office. The master list will be used to track the results of the study participant's data collection.

An Excel spread sheet will be used to collect this information using only the participants unique study number and stored electronically on a CAC PIN protected computer in the PI's locked office.

All data and PII will be destroyed (shred or deleted) at the conclusion of this project.

Risks:

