To satisfy these two areas of responsibility, the research monitor may discuss the research protocol with the investigators, interview study subjects, and consult with others outside of the project about the research. In the event a problem is identified, they have authority to stop a research protocol in progress, remove individual subjects from a study, and take whatever steps are necessary to protect the safety and well-being of subjects until the IRB can assess the monitor's report.

Research monitors are required to promptly report their medical monitoring and oversight monitoring observations and findings to the IRB or other designated official.

Data Collection Sheets

See attached Excel spreadsheet.

Objectives:

The obstetrics literature to date focuses on TXA use prior to non-emergent cesarean delivery or in response to hemorrhage. Data is lacking in the area of prophylactic use prior to vaginal delivery. The aim of this study will be to assess the ability of TXA to prevent postpartum hemorrhage.

Primary Outcome:

To assess the efficacy of TXA in reducing the incidence of postpartum hemorrhage when given prophylactically prior to all deliveries.

The American Congress of Obstetricians and Gynecologists published 'ReVitalize' in 2014 that defined postpartum hemorrhage as blood loss of ≥ 1000 cc or blood loss accompanied by sign/symptoms of hypovolemia to include blood transfusion within 24 hours following the birth process (includes intrapartum loss).

[figure not shown]
For the purposes of this study, postpartum hemorrhage will be defined as a blood loss of ≥ 1000 cc in addition to all patients requiring blood transfusion (even if blood loss is less than 1000cc).

Secondary outcomes:

Estimated blood loss (EBL) – measured in cubic centimeters. EBL will be decided upon by the delivery provider. All delivering providers at this institution have received formal instruction on estimation of blood loss and a visual aid is available at every bedside and in the operating room (see below).

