Appendix L

Examples of Estimating Blood Loss

Zuckerwise. Estimated Obstetric Blood Loss With Visual Aid. *Obstet Gynecol* 2014.

Delivering providers will also adhere to NAVMEDWESTINST 6320.20, which specifies that once an EBL reaches 500cc, the delivering provider will move from an *estimation* of blood loss to utilizing a *quantitative* blood loss (QBL). QBLs are obtained by the weighing of chux pads, drapes, and linens that have been soiled (after first calibrating the scale to remove the original weight of the contaminated product). It also includes the blood that has been collected in the suction canister in the operating room.

In instances when EBL is decided upon at delivery, and ongoing bleeding occurs after the provider has left the room (and is called back), a QBL should be obtained. The QBL should be added to the initial EBL for a *cumulative* blood loss (CBL).

Percent decrease in hematocrit (Hct) – The percent change of the patients' Hct obtained on admission from that obtained after delivery. A post-operative Hct is routinely obtained six hours following a cesarean delivery. A Hct is not routinely obtained for patients having a vaginal delivery unless EBL exceeds 500cc. A post vaginal delivery Hct will not be obtained in patients for the sole purpose of this research study.

Rates of blood transfusion – The number of patients requiring blood transfusion divided by the total number of deliveries.

The types and amounts of products transfused – in patients requiring transfusion, the type of product (i.e, packed red blood cells, whole blood, fresh frozen plasma, platelets, and cryoprecipitate) will be recorded, along with how many of each type they received.

The use of uterotonic agents – in patients requiring uterotonic agents beyond the first bolus of oxytocin (i.e. second bolus of oxytocin, methylergonovine, 15-methyl Prostaglandin F_{2α}, misoprostol) will be recorded, along with how many doses of each

The need for surgical intervention – the number of patient's that require surgical intervention following a vaginal delivery for the purposes of controlling excessive blood loss divided by the total number of vaginal deliveries

The need for reoperation - the number of patients that require return to the operating room following a cesarean delivery for the purposes of controlling excessive blood loss divided by the total number of cesarean deliveries

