3. Begin the TXA infusion directly following umbilical cord clamping for the intent of preventing postpartum hemorrhage.
 - a. The TXA may be run as a secondary line (i.e. is compatible with pitocin) per [name], Chairman of the Pharmacy Department
4. TXA should be administered in a separate IV line from blood products.
5. Two-person verification is required (this can be a second nurse or can be the physician or certified nurse midwife that is attending the delivery)
6. A single additional dose of TXA (1 gram IV over 10 minutes) can be repeated after 30 minutes if bleeding continues or if bleeding stops and then re-starts within 24 hours of the first dose (for a maximum dose of 2g in 24 hours). This additional dose is considered a treatment dose. This additional dose is not required by the study design, which is to assess TXA in the *prevention* of hemorrhage.

Supplement B: Patient Monitoring following delivery

1. After delivery patients will be observed on the Labor and Delivery floor for a minimum of one hour. Thereafter they will be transferred to the postpartum ward where they will be observed for a minimum of 24 hours.
2. The following physical assessments will be completed every 15 minutes x 1 hour , then every 30 min x 2 hours, then every 4 hours until discharge.
 - A. Vital signs: BP and pulse as above. Temperature Q1 hour (after 2 normal values will space to Q4 hours).
 - B. Fundal assessment: Placement and tone
 - C. Lochia assessment: Color, with or without clots, amount
 - D. Perineum assessment: Intactness (approximation of tissues/wound/lacerations), hematomas, swelling
 - E. Bladder assessment: Distention, voiding (noting/documentation of most recent void/amount, spontaneous/catheterization).
 - F. Any symptoms that the patient reports.
3. The nursing staff will immediately report any findings that are not within normal limits to the delivering provider or on-call provider:
 - A. BP systolic > 160 or < 100
 - B. BP diastolic > 90 or <50
 - C. Pulse > 100
 - D. Nausea, dizziness or SOB
 - E. Moderate to copious lochia
 - F. Increased swelling or pain in vagina or perineal/rectal area
 - G. Distended bladder not relieved by catheterization or patient voiding
 - H. Fundus displaced or above umbilicus (if differs from initial normal placement of uterus), unrelieved with empty bladder.
4. Documentation
 - A. All assessments are documented in Essentris. See below for notes needed:
 - B. Complete intake and output flow sheet

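### Blood loss is compared with historic records by an unadjusted t-test over vaginal and cesarean births together, so a change in cesarean share would bias the result and pooling costs precision

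*Combined protocol and SAP*

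**What the plan says.** The statistical paragraph appears twice, under Research Design (Statistical Analysis) and under Study Procedures (Data Analysis). Both state "Normal distribution will be assumed given the intended number of patients for analysis" and then "The t-test will be utilized for the comparison of continuous interval data". Neither names a covariate, a model or a split by delivery mode.

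The design is "Methods: One Arm". The comparator is historical: "The data collected will be measured against the historic PPH rates of NMCSO over a period of time to be determined". For secondary outcomes, Study Procedures adds a chart review of the 12 months before the protocol starts (Data collection) and record sampling to estimate institutional rates (Data Analysis). The number of charts is not given.

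The primary outcome section covers all deliveries. Estimated blood loss is the first secondary outcome listed, is not divided by mode, and is a provider's judgement: "EBL will be decided upon by the delivery provider". It gives way to weighed loss once the estimate reaches 500 cc.

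On mode itself:
- The variable list includes "planned mode of delivery, mode of delivery".
- Two secondary outcomes have mode-specific denominators; reoperation, for example, is "divided by the total number of cesarean deliveries".
- Supplement A, item 3 sets the timing: "Begin the TXA infusion directly following umbilical cord clamping".
- The only confounder named is third-stage management.
- The risk categories that will stratify primary and secondary outcomes include prior cesarean but not the mode of the current delivery.

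**The concern.** If cesarean and vaginal births differ in usual blood loss, a pooled comparison has two problems.

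The first is bias. Nothing in a one-arm study with a historical comparator makes the cesarean share equal in the two periods. Consent at prenatal visits and the exclusion list may also select a different mix from the one in the charts. A lower share in the treated cohort would look like a drug effect, and a higher share would hide one.

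The second is precision. Even with equal shares, the gap between modes adds to the variance of the pooled comparison and has nothing to do with TXA.

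Mode is a legitimate covariate because it is settled before the infusion begins, so adjusting for it removes no part of the treatment effect. The outcome matters: at the planned rates the primary outcome yields only 890 × 0.0143 = 13 to 890 × 0.0286 = 25 events, so readers are likely to lean on blood loss.

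**Working it through.** **The plan's own figure.** The 890 concerns the binary primary outcome. It reproduces as a one-sample test of 2.86% against 1.43% (two-sided 5% and 80% power, which the plan does not state):

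n = [(1.960 × √(0.0286 × 0.9714) + 0.842 × √(0.0143 × 0.9857)) / 0.0143]² = 890.

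Nothing below changes it.

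**Assumed inputs.** The documents give no cesarean share, mean loss by mode, SD or historic sample size. For illustration: gap between modes g = 400 cc, within-mode SD s = 250 cc, historic cesarean share 30%, and 890 women in each cohort.

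**Bias.** With no treatment effect, the expected pooled difference is (difference in share) × g. For 25% v 30% it is −0.05 × 400 = −20 cc.

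Variance per woman is s² + c(1−c)g², where c is the cesarean share:
- treated: 62,500 + 0.1875 × 160,000 = 92,500
- historic: 62,500 + 0.21 × 160,000 = 96,100
- SE = √((92,500 + 96,100)/890) = 14.6 cc

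The shift is 20/14.6 = 1.37 SEs. The chance that a nominal 5% test rejects is Φ(−1.96 + 1.37) + Φ(−1.96 − 1.37) ≈ 0.28. Simulations with 890 v 890 gave about 26–28% unadjusted and about 5% with mode in the model.

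The same formula for other assumptions, with no treatment effect:

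| Treated v historic share | Gap, SD (cc) | Bias (cc) | SE (cc) | Rejection |
|---|---|---|---|---|
| 30% v 30% | 400, 250 | 0 | 14.7 | 5% |
| 27% v 30% | 400, 250 | −12 | 14.6 | 13% |
| 25% v 30% | 300, 250 | −15 | 13.4 | 20% |
| 25% v 30% | 400, 300 | −20 | 16.5 | 23% |
| 20% v 30% | 400, 250 | −40 | 14.4 | 79% |

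If the cohort were instead tested against one fixed institutional mean, the bias for 25% v 30% would stay at −20 cc (gap 400, SD 250). The SE would be √(92,500/890) = 10.2 cc and the rejection rate about 50%.

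The bias can also hide benefit. With 35% v 30% and a true 33 cc reduction, the expected pooled difference is −33 + 20 = −13 cc. The treated variance is 62,500 + 0.2275 × 160,000 = 98,900, so the SE is √((98,900 + 96,100)/890) = 14.8 cc and power about 14%. Simulated power was about 13% unadjusted and 79% adjusted.

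**Precision when the mix is equal.** The share of information lost by ignoring mode is R² = c(1−c)d² / (1 + c(1−c)d²), with d = g/s.
- Low end (c = 0.15, d = 0.5): 0.0319/1.0319 = 3%.
- High end (c = 0.35, d = 2.5): 1.4219/2.4219 = 59%.
- Illustration (c = 0.30, d = 1.6): 0.5376/1.5376 = 35%. The SE falls from √(2 × 96,100/890) = 14.7 cc to √(2 × 62,500/890) = 11.9 cc.

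**A check against the plan's own rate.** If loss is log-normal within mode with means 350 and 750 cc, SD 250 cc and 30% cesarean, 6.2% of women would reach 1000 cc. The plan's institutional hemorrhage rate is 2.86%, and its definition also counts transfused women. The illustration is therefore not calibrated to this hospital. Recalibrating does not push R² one way: a smaller gap lowers it and a smaller SD raises it.

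**The case against.** The strongest objection is that the adjustment needs data the plan does not clearly promise. The chart review is meant to yield institutional rates, and the mode-specific denominators could be met from delivery totals. Against a single overall mean, a regression on mode cannot be run. This stands. A reader might infer that adjustment costs nothing, as in a randomized trial that already holds the covariate; here blood loss and mode must be linked woman by woman in the historic sample. The added work is modest, because the chart review is already planned and those denominators already call for historic mode in some form.

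A reader might also infer that a fifth to a half of the information is lost. The documents do not support that band. It is a plausible middle of the 3–59% range, but at 30% cesarean it needs a gap of about 1.1 to 2.2 within-mode SDs, and the plan gives neither gap nor SD. The 890 historic charts are likewise an assumption.

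The t-test sentence is generic, and the planned risk strata include factors that probably track cesarean delivery, such as previa and prior cesarean. They may recover part of the variance and the bias. How much is unknown: current mode is not among them, and the plan does not say how the strata enter any test.

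Two further limits stand. Recorded blood loss mixes visual, weighed and cumulative measures, which this change does not cure. Blood loss is also a secondary outcome for which the plan claims no power.

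**Conclusion.** The concern holds for blood loss, chiefly on grounds of bias and secondly on precision. The documents establish the structure: one arm, historic comparator, both modes pooled, no covariate, and mode recorded and settled before exposure. They do not establish the size. Under the stated assumptions, a 5-point difference in cesarean share gives about 20 cc of bias and a false-positive rate of about 26–28% instead of 5%. The other scenarios with unequal shares run from 13% to 79%. If the shares happen to be equal, only the loss of precision remains, and 3–59% is as narrow as it can be stated. Adjustment for mode removes the delivery-mix bias only; other differences between the two periods remain. This is a change that should be made, but it does not undermine the primary analysis.

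**What to change.** In the planned historic chart review, abstract for each sampled woman her recorded blood loss and her actual mode of delivery, and state how many charts will be sampled.

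In both copies of the statistical paragraph, replace the t-test for blood loss with a linear regression of recorded blood loss on cohort (TXA or historic) and actual mode (vaginal or cesarean), with robust standard errors. Report the adjusted mean difference in cc with its 95% confidence interval, and show the cesarean share of each cohort beside it so that a shift in mix is visible.

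The cost is small: patient-level abstraction of two fields in the historic sample and a short change to the analysis text. Participants need no new data, and the sample size does not change. The report should say that confounding by period other than delivery mix is not removed.

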- Rare events from worldwide post marketing reports have included thromboembolic events (e.g., deep vein thrombosis, pulmonary embolism, cerebral thrombosis, acute renal cortical necrosis, and central retinal artery and vein obstruction), convulsion, chromatopsia, and visual impairment

Radiation/Laser Exposure: None

Justification/Minimization of Risks:

All identifiers will remain in the protected medical record. Any PHI extracted as a result of this study will be destroyed at the earliest opportunity consistent with conduct of the research, unless there is a health or research justification for retaining the identifiers or such retention is otherwise required by law. Protected health information will not be reused or disclosed to any other person or entity, except as required by law, for authorized oversight of the research study, or for other research for which the use or disclosure of protected health information would be permitted by approval of the IRB.

The current Maternal Child Executive Committee Policy on Tranexamic Acid (TXA) Administration will be followed to minimize any risks of harm to subjects.

Benefits:

Potential benefits of the research to the subject include a reduction in blood loss from delivery, decreased need for uterotonic medications, decreased need for blood transfusion, and less morbidity as a result of symptomatic anemia, resulting in increased satisfaction with the postpartum experience and increased maternal-neonate interactions.

Potential benefits of the research to the community/society included less overall maternal morbidity/mortality as well as a decreased demand on limited resources (i.e. blood products, uterotonic medications, time of additional healthcare providers, etc).

Requirements for Research Monitor:

Research Monitor Responsibilities:

Serves as a medical monitor, reviewing AEs as they are discovered to determine if the events suggest a trend toward increased risk to subjects that would require additional safeguards, subject notifications, or an invoking of stopping rules.

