Rates of hysterectomy – the number of patients requiring hysterectomy divided by the total number of deliveries

Admission to the Intensive Care Unit (ICU) - the number of patients requiring admission to the intensive care unit secondary to excessive blood loss divided by the total number of deliveries

Neonatal outcomes – incidence of fetal anemia, infection, hyperbilirubinemia, neurologic outcomes, and neonatal intensive unit admissions

Maternal mortality – incidence of mortality

Additionally, postpartum hemorrhage risk assessment will be utilized to stratify patients with regard to primary and secondary outcomes.

- Patients will be risk stratified to one of three risk categories depending on admission and intrapartum risk factors
 - High Risk Factors:
 - Placenta previa/ low lying placenta
 - Suspected accreta or percreta
 - Platelet count <70,000
 - Active bleeding
 - Known coagulopathy
 - Two or more medium risk factors
 - Medium Risk Factors:
 - Prior cesarean delivery, uterine surgery, or multiple laparotomies
 - Multiple gestation
 - > 4 prior births
 - Prior obstetric hemorrhage
 - Large myomas
 - EFW >4000
 - BMI > 40
 - Hct < 30%
 - Chorioamnionitis
 - >24 hours on Oxytocin
 - Magnesium sulfate
 - Low Risk: all patients not falling in the medium or high risk categories

Importance to Navy Medicine:

Beyond the potential impact that this study has in the reduction of maternal morbidity and mortality, it can also allow for perspective into resource management. Some of the Navy Military Treatment Facilities (MTFs) have limited blood bank stock, and massive hemorrhages requiring ongoing transfusion of products can quickly deplete the entirety of the supply. If we can find a solution that will reduce the number of instances where transfusion is necessary we can help to preserve limited resources. Likewise, this preventive measure will also have the potential to (cost) reduce the need for additional uterotonics, personnel, supplies and ICU beds.

There will be no collaboration with outside institutions.

Supplement A: TXA Protocol Administration (Modified from the NMCS Maternal Child Executive Committee's Policy)

1. TXA comes in a 1000 mg/10 mL vial. Nursing staff will pull this from the Pyxis at the same time they bring Oxytocin into the L&D room.
2. Add 1000 mg (or 1 vial) of 1000 mg/10 mL to 100 mL normal saline (100 mg/mL)
 - a. Bolus: 1 gram IV over 10 minutes
 - i. Set infusion pump rate to 600 mL/hr

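### The plan has no means to show that the historic comparator had the same third-stage care as participants or was free of preventive TXA

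*Combined protocol and SAP*

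**What the plan says.** The study has one arm (Research Design, Methods). Under Source of the data, the results are to be set against the hospital's historic PPH rates over a period still to be chosen.

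- **Named confounder.** The section Confounding variables has one entry: "Management of the 3rd stage of labor". The Background says that routine third-stage oxytocin reduces the risk of excessive blood loss.
- **Historic data.** Study Procedures, 3. Data collection, item 5: "Chart review will be performed to estimate institutional rates of the secondary outcomes in the 12 months preceding the initiation of the protocol". Data Analysis item 3 adds that institutional rates come from record sampling. No treatments or covariates are listed for historic women.
- **Nearest historic item.** Among the secondary outcomes, uterotonic use is counted only beyond the first oxytocin bolus.
- **Analysis.** Chi-square tests and t-tests, with outcomes also stratified by PPH risk category.
- **TXA policy.** Justification/Minimization of Risks: "The current Maternal Child Executive Committee Policy on Tranexamic Acid (TXA) Administration will be followed to minimize any risks of harm to subjects". The title of Supplement A describes its regimen as "Modified from the NMCS Maternal Child Executive Committee" policy. The policy's start date, indications and uptake are not given.
- **Study question.** The primary outcome concerns TXA given prophylactically. Supplement A allows one discretionary further dose and classes it as treatment, not prevention.

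**The concern.** With no concurrent control, the comparison is only as good as the match in background care between the two periods. The plan identifies one aspect of that care as a confounder and then gives no way to examine it. If third-stage practice changed between periods, the change would be credited to TXA, or would offset a TXA effect.

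The current TXA policy raises a second question. If some historic women received TXA preventively, the historic rate is partly a treated rate and the apparent benefit shrinks. If some received it as treatment, that may simply be background care shared with participants, but a reader can judge this only if it is recorded in both periods.

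**Working it through.** **1. Is the background recorded and used?**

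- First-line third-stage care in historic women: not among the data to be obtained. The uterotonic outcome starts after the first oxytocin bolus, and it is an aggregate rate, not a covariate.
- First-line third-stage care in participants: the variable list has oxytocin use and uterotonic use, without reference to the third stage or to timing.
- Third-stage care in the analysis: none. The risk strata contain no third-stage factor; the closest, more than 24 hours on oxytocin, is listed as a medium risk factor and is not third-stage care.
- TXA: not in the variable list, so neither historic use nor a participant's treatment dose is named as an item to collect.

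**2. The plan's own figure.** Study Procedures, 4. Data Analysis, item 2 takes an institutional PPH rate of 2.86%, gives "a desired impact of reducing the hemorrhage rates by 50% after implementation of the new protocol" as the aim, and arrives at 890 women. So p0 = 0.0286 and p1 = 0.0143. Alpha, sidedness and power are not stated; two-sided 5% and 80% are assumed here. For one sample against a fixed rate:

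n = [(z_a √(p0(1−p0)) + z_b √(p1(1−p1))) / (p0−p1)]²
= [(1.960 × 0.1667 + 0.842 × 0.1187) / 0.0143]² ≈ 890.

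One-sided 5% with 90% power fits about as well (889). A two-sample calculation does not fit (1,611 per group at two-sided 5%, 80% power). The sample size therefore treats 2.86% as a known rate on the same background.

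Expected events in 890 women: 890 × 0.0286 = 25.5 with no effect, and 890 × 0.0143 = 12.7 at the target.

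**3. If background care alone lowered PPH (assumed shifts, no TXA effect).** Exact binomial, n = 890. The largest count with lower-tail probability of at most 2.5% at 2.86% is 15.

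| Background change | True rate | P(15 or fewer events) |
|---|---|---|
| none | 2.86% | 1.7% |
| 10% lower | 0.90 × 2.86% = 2.57% | 5.2% |
| 20% lower | 0.80 × 2.86% = 2.29% | 13.6% |

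If the intended test is one-sided 5%, the cut-off is 17 events and the three probabilities are 4.9%, 12.3% and 26.7%.

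**4. If historic women had preventive TXA (assumed).** Suppose TXA halves PPH risk and a share s of historic women received it preventively. The reduction still visible against the historic rate is 1 − 0.5/(1 − 0.5s).

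- s = 1/3: 1 − 0.5/0.833 = 40%; power falls from 80% to about 54%.
- s = 4/7 (57%): 1 − 0.5/0.714 = 30%; power falls to about 31%.

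These powers use the normal approximation at two-sided 5%. The shares are large, so a serious loss of power requires preventive use to have been common.

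**The case against.** A reader might infer that historic women did receive TXA, so that the study is not comparing TXA with no TXA. The documents do not support that. They show that a policy is current, not when it began, what it covered or how often it was used. Nor do they show any change in third-stage care. The Background calls third-stage oxytocin recommended for all women, and Supplement A has oxytocin brought to the room along with the TXA, which suggests little variation. That lowers the likelihood of the problem. It does not remove the gap, because a general recommendation is not a record of this hospital's practice and the plan itself lists the item as a confounder.

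The plan also does not claim a contrast of TXA with no TXA whatsoever. Its question is prevention, with a separate treatment dose. Treatment TXA in both periods could be common background, so it does not follow that such use hides a preventive benefit. A specific dilution of the transfusion, surgery or ICU rates from treatment TXA would rest on assumed uptake and assumed effect, with no anchor in the documents, and no such figure is relied on here.

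The collection spreadsheet is referred to but not shown, so it cannot be said that first-line care goes wholly unrecorded in participants. The entry on third-stage management could also be read as something to be collected. Neither reading provides historic values or a use in the analysis.

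Finally, a 10% or 20% background shift could stand for any drift over time, and with so few events adjustment will be imprecise. Both points stand. They are reasons to keep the adjusted comparison as supporting evidence.

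**Conclusion.** The point holds as a gap in what the plan can demonstrate, not as a demonstrated bias. The plan names one confounder, does not provide for extracting it in historic deliveries and does not use it. It also has no means to show that the historic comparator was free of preventive TXA.

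The direction is open. Under assumed background reductions of 10% and 20%, the chance of wrongly finding a benefit rises from 1.7% to 5.2% and 13.6%. Preventive TXA in the historic period would act the other way. These sizes depend on testing 890 women against a fixed 2.86% at two-sided 5%, which the documents do not state but which reproduces their sample size. The documents give no exposure figures for either period. The change is a cheap improvement that should be made before the historic data are extracted.

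**What to change.** 1. In the chart review under Data collection item 5, also extract for each historic delivery: PPH status by the study definition; first-line third-stage uterotonic (given or not, drug, timing relative to delivery); and any TXA (given or not, preventive or treatment, timing). Record the same items with the same definitions for participants.
2. Exclude historic women given preventive TXA from the comparator. Report treatment TXA in both periods without excluding those women, since excluding them would select on bleeding. State the contrast as preventive TXA added to usual care.
3. Tabulate third-stage management by period. If it differs, give a comparison adjusted for it, or restricted to like management, as a supporting analysis beside the crude test.
4. Separately, reconcile the statement that the current policy will be followed with Supplement A, which is a modification of that policy, so that it is clear which document governs participants.

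**Cost.** A few more fields in a review already planned. Individual historic PPH status is an addition, because the review as described covers only secondary-outcome rates. Some timings will be missing. With about 13 to 25 events among participants, adjusted or restricted estimates will be imprecise and some strata may be nearly empty.
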